3.8.2. Baseline radiological variables

Baseline imaging variables assessed will be:

- Single or multiple intracranial meningioma
- Tumour signal intensity compared to the contralateral grey matter on fluid attenuated inversion recovery (FLAIR) and T2-weighted (T2) MRI (hypo/iso/hyper) (Figure 2)
- Peritumoural signal intensity in relation to tumour volume using the signal change present on FLAIR and T2 MRI (0-5%/6-33%/34-66%/67-100%; adapted from the VASARI [Visually AcceSAbLe Rembrandt Images] MR features for gliomas (20))
- Meningioma volume using the ABC/2 formula on contrast-enhanced T1-weighted MRI/CT: (A) maximum meningioma diameter on axial plane, (B) diameter perpendicular to (A) and (C) maximum height on coronal/sagittal plane, not taking into the account the dural tail
- Meningioma location classed into non-skull base and skull base and further subcategorised according to the ICOM (International Consortium on Meningioma) classification system (Appendix 2)
- Proximity to major dural venous sinuses (superior sagittal sinus/transverse sinus/sigmoid sinus/cavernous sinus/the confluence of sinuses) categorised as separate (within 10 mm), in direct contact with its wall, or invading, excluding the dural tail (Figure 2)
- Contact with critical neurovascular structures (i.e. internal carotid artery and optic apparatus)

Meningiomas that fulfil one of the two previous categories are said to be in proximity to critical neurovascular structures. A video manual prepared by the study team will be made available to assist with standardisation and quality assurance of scan interpretation across participating centres.

[figure not shown]

Figure 2. (A-C) T2 MR axial sequences showing the 3 levels of tumour intensity (circle). (A) Hypointense. (B) Isointense. (C) Hyperintense. (D-F) T1-weighted MR with gadolinium (contrast) showing the relationship between the meningioma and the nearby venous sinus (SSS). (D) Separate as there's no clear attachment to the sinus wall. (E) In direct contact with the lateral wall of the sinus. (F) Clear macroscopic distortion and invasion of the sinus.

3.8.3. Management strategy

Management strategies will include active monitoring and intervention (surgery, stereotactic radiosurgery (SRS), fractionated radiotherapy (fRT) or discharge from outpatient clinic care) (Figure 3). **Active monitoring** is defined as regular surveillance imaging and outpatient clinical observation. Recorded factors will include:

- Number of scans, and interval between them (months)
- For each scan: peritumoural signal intensity, venous sinus involvement and meningioma volume
- Each scan will be examined alongside its corresponding outpatient clinic appointment for any evidence of meningioma-related symptoms (motor/sensory/language/cognitive/seizure/headache/other)
- The outcome of each clinical encounter (i.e. outpatient appointment) will be recorded (resume follow-up/surgery/SRS/fRT/hospital discharge)

Intervention details; if performed, will also be recorded. These will include indication for intervention (clinical-radiological/clinical/radiological/patient preference) and time to intervention. For patients treated with clinical-radiological or clinical progression, status of meningioma-related neurological morbidity will be noted.

For surgery, the following will additionally be recorded:

- Simpson grade (as recorded by the surgeon in the operative notes) (21)
- WHO grade (classified according to the WHO system in use at the time of surgery and updated according to the WHO 2016 classification dependent on pathologists' availability (22)) and presence of any reported brain invasion (yes / no / not reported)
- Postoperative medical and surgical complications recorded at 30 days (Landriel-Ibañez Classification (Table 3) (23))
- Follow-up duration (months)
- WHO performance status pre- and postoperatively and at the last follow-up appointment.
- Recurrence on contrast-enhanced MRI during that time (yes/no) and if recurred then the time to recurrence

For SRS and fRT:

- Fractionated dose (fRT), number of fractions (fRT) and total dose (fRT /SRS)
- Early and late (≥ 3 months) toxicity (assessed by CTCAE v5.0, https://ctep.cancer.gov/protocoldevelopment/electronic_applications/ctc.htm)
- Duration of follow-up post-radiation (months)
- WHO performance status pre- and post-radiation and at the last follow-up appointment
- Progression/regrowth on contrast-enhanced MRI during that time (yes/no) and if progressed/regrew then the time to progression/regrowth

For patients discharged from outpatient care, data sources will be checked for any readmissions/rescans thought to be attributed to the incidental meningioma within the study timeframe; date of diagnosis up to the date of data entry. Outcome following readmissions/rescans will be noted.

Grade I	Any non–life-threatening deviation from normal postoperative course, not requiring invasive treatment
Grade Ia	Complication requiring no drug treatment
Grade Ib	Complication requiring drug treatment
Grade II	Complication requiring invasive treatment such as surgical, endoscopic, or endovascular interventions
Grade IIa	Complication requiring intervention without general anaesthesia
Grade IIb	Complication requiring intervention with general anaesthesia
Grade III	Life-threatening complications requiring management in ICU
Grade IIIa	Complication involving single organ failure
Grade IIIb	Complication involving multiple organ failure
Grade IV	Complication resulting in death
Surgical Complications	Adverse events that are directly related to surgery or surgical technique
Medical Complications	Adverse events that are not directly related to surgery or surgical technique
Suffix “T” (Transient)	New neurologic deficit improving within 30 days of surgical procedure; can be added to each grade of complication
Suffix “P” (Persistent)	New neurologic deficit extending beyond 30 days of surgical procedure; can be added to each grade of complication

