3 METHODS

3.1. Study design

This will be a retrospective, international multicentre cohort study. The study will include incidental meningioma patients managed at each participating centre. Cases will be identified by the local site research teams using existing patient medical records. Baseline clinical and radiological characteristics, tumour management, and clinical and radiological outcomes will be collected and recorded (anonymised data) on a secure database by the local investigator. Since this study falls within the remit of clinical outcomes audit, individual patient consent is not required. The study will collect data from the medical records for patients newly-diagnosed over a 2-year period between 1st January 2009 and 31st December 2010. This is an observational study and will not impact on routine patient care.

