Two competing risk analyses will be performed. One assessing the cumulative incidence rate (CIR) of primary intervention at different time points following diagnosis stratified by PS and ACCI groups and the other will evaluate the CIR of disease progression. The competing event for the former will be non-meningioma-specific mortality either observed during follow-up or after being discharged from outpatient care. Patients who remain under follow-up will be censored at the last outpatient clinic appointment. Patients discharged alive from outpatient care will be censored at the last time they were seen by a healthcare physician up to the date of data entry.

For the disease progression analysis, mortality after hospital discharge could not be used as a competing event as the time interval between discharge and death could have seen radiological changes which meet the disease progression definition. Instead, four events will

be considered competing in nature, discharge from outpatient care, loss to follow-up, death during follow-up or an intervention before disease progression occurred with the first three grouped together. Censoring will only be done for patients who remain under follow-up at the last clinic appointment. To test the equality across CIR groups, the Fine and Gray test will be carried out. Plots of CIRs and 95% confidence intervals (CIs) will also be generated and compared to the training data set (11).

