9 APPENDICES

9.1. Appendix. 1. Guide for REDCap database developers

Characteristic	Options	Notes
BASELINE CLINICAL CHARACTERISTICS (PAGE/SECTION 1)		
Age (years)	Free field	Required entry
Sex	Dropdown list/check box 
 • Male • Female 	
Ethnicity	Dropdown list/check box 
 • White • Mixed / Multiple ethnic groups • Asian / Asian British • Black / African / Caribbean / Black British • Other ethnic group • NA 	Required entry. Allow one option only. Other ethic group prompts a free text box
Comorbidities	Check box 
 • Hypertension - systolic > 140 or diastolic > 90 and patients on medical treatment • Previous myocardial infarction • Congestive heart failure • Peripheral vascular disease • Previous stroke/TIA - If hemiplegia present, do not check • Hemi/paraplegia • Diabetes which requires medical treatment 	Required entry. Allow multiple options. Note to data collector: Age and comorbidities will be used to calculate the age adjusted Charlson comorbidity index. Each of these is defined in the guide provided

	
 • Diabetes with end-organ damage - if so, do not check diabetes that requires treatment • COPD/Asthma • Renal disease • Mild liver disease - Hep B/C or cirrhosis without portal hypertension • Moderate to severe liver disease - cirrhosis with portal hypertension, jaundice, ascites • Peptic ulcer disease • Cancer - excluding basal cell carcinoma • Metastatic cancer - if so, do not check cancer • Rheumatic or connective tissue disease • HIV/AIDS • Skin ulcers/cellulitis • Depression • Dementia • On Warfarin 	
WHO Performance status	Dropdown list/check box 
 • 0 • 1 • 2 • 3 • 4 	Required entry. Allow one option only
Indication for scan	Dropdown list/check box 
 • Headache • Cerebrovascular accident • Head injury • Audiovestibular symptoms 	Required entry. Allow multiple options. Note to data collector: The meningioma must not be thought to be the cause of these symptoms. Other indications might include lethargy, research, sinusitis, anosmia...etc. Other prompts a free text box

	
 • Visual symptoms • Psychiatric symptoms • Cognitive symptoms • Loss of consciousness • Other 	
NUMBER OF MENINGIOMAS ON 1ST DIAGNOSTIC SCAN (PAGE/SECTION 2)		
Initial scan date	DD/MM/YYYY	Required entry. YYYY can't be ≤2007 or ≥2011

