WHO PS at time of recurrence/last follow-up	Dropdown list/checkbox 
 • 0 	Prompt entry if previous option (Postoperative WHO PS) is not 5

	
 • 1 • 2 • 3 • 4 	
SRS (SECTION/PAGE 7)		
Pre-radiation WHO PS	Dropdown list/check box 
 • 0 • 1 • 2 • 3 • 4 	Required entry. Allow one option only
Pre-radiation comorbidity	Check box 
 • Hypertension - systolic > 140 or diastolic > 90 and patients on medical treatment • Previous myocardial infarction • Congestive heart failure • Peripheral vascular disease • Previous stroke/TIA - If hemiplegia present, do not check • Hemi/paraplegia • Diabetes which requires medical treatment • Diabetes with end-organ damage - if so, do not check diabetes that requires treatment • COPD/Asthma • Renal disease • Mild liver disease - Hep B/C or cirrhosis without portal hypertension 	Required entry. Allow multiple options. Note to data collector: Age and comorbidities will be used to calculate the age adjusted Charlson comorbidity index. Each of these is defined in the guide provided

	
 • Moderate to severe liver disease - cirrhosis with portal hypertension, jaundice, ascites • Peptic ulcer disease • Cancer - excluding basal cell carcinoma • Metastatic cancer - if so, do not check cancer • Rheumatic or connective tissue disease • HIV/AIDS • Skin ulcers/cellulitis • Depression • Dementia • On Warfarin 	
Dose	Free field	Required entry
Early CTCAE toxicity (≤3 months)	Checkbox	Required entry
Toxicity	Free field	
Prompt entry if previous option (Early CTCAE toxicity (≤3 months)) is ticked
 
Note to data collector: https://ctep.cancer.gov/protocoldevelopment/electronic_applications/ctc.htm Use the following format: System class organ (SOC)-CTCAE term-grade e.g. nervous system disorders-headache-1. Select the complication with the highest toxicity grade

Late CTCAE toxicity	Checkbox	Required entry
Toxicity	Free field	
Prompt entry if previous option (Late CTCAE toxicity) is ticked
 
Note to data collector: https://ctep.cancer.gov/protocoldevelopment/electronic_applications/ctc.htm Use the following format: System class organ (SOC)-CTCAE term-grade e.g. nervous system disorders-headache-1. Select the complication with the highest toxicity grade

Meningioma progression/regrowth	Checkbox	Required

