Scan date (at progression or last follow-up date if no progression)	DD/MM/YYYY	Required
WHO PS at time of progression/last follow-up	Dropdown list/checkbox 
 • 0 • 1 	Required. Allow one option only

	
 • 2 • 3 • 4 • 5 (dead) 	
fRT (SECTION/PAGE 8)		
Pre-radiation WHO PS	Dropdown list/check box 
 • 0 • 1 • 2 • 3 • 4 	Required entry
Pre-radiation comorbidity	Check box 
 • Myocardial infarction • Congestive heart failure • Peripheral vascular disease • Hemiplegia • Cerebrovascular disease • Pulmonary disease • Diabetes • Renal disease • Liver disease • Peptic ulcer disease • Cancer • Dementia • Connective tissue disease • AIDS • Hypertension • Skin ulcers/cellulitis • Depression • On Warfarin 	Required entry. Allow multiple options. Note to data collector: Age and comorbidities will be used to calculate the age adjusted Charlson comorbidity index. Each of these is defined in the guide provided
Number of fractions	Free field	Required entry
Fractionated dose	Free field	Required entry
Total dose	Free field	Required entry
Early CTCAE toxicity (≤3 months)	Checkbox	Required entry
Toxicity	Free field	Prompt entry if previous option (Early CTCAE toxicity (≤3 months)) is ticked

		Note to data collector: https://ctep.cancer.gov/protocoldevelopment/electronic_applications/ctc.htm Use the following format: System class organ (SOC)-CTCAE term-grade e.g. nervous system disorders-headache-1. Select the complication with the highest toxicity grade
Late CTCAE toxicity	Checkbox	Required entry
Toxicity	Free field	Prompt entry if previous option (Late CTCAE toxicity) is ticked Note to data collector: https://ctep.cancer.gov/protocoldevelopment/electronic_applications/ctc.htm Use the following format: System class organ (SOC)-CTCAE term-grade e.g. nervous system disorders-headache-1. Select the complication with the highest toxicity grade
Meningioma progression/regrowth	Checkbox	Required
Scan date (at progression or last follow-up date if no progression)	DD/MM/YYYY	Required
WHO PS at time of progression/last follow-up	Dropdown list/checkbox 
 • 0 • 1 • 2 • 3 • 4 • 5 (dead) 	Required. Allow one option only
Discharge from outpatient care/Lost to follow-up (SECTION/PAGE 9)		
Date of data entry into the database	DD/MM/YYYY	Required entry

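### Appendix 1 has no fields for the radiation treatment dates, the indication for radiation, or the clinic-contact, discharge and loss dates that sections 3.8.3 and 3.10.1 rely on

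*Protocol*

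**What the plan says.** Section 3.8.3 covers surgery, SRS and fRT together and states: "These will include indication for intervention (clinical-radiological/clinical/radiological/patient preference) and time to intervention". For SRS and fRT it also asks for performance status before and after radiation and at last follow-up, the length of follow-up after radiation, and the time to progression or regrowth.

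Section 3.10.1 plans two competing-risk analyses. The first is described as "One assessing the cumulative incidence rate (CIR) of primary intervention at different time points following diagnosis", and for it the rule is: "Patients who remain under follow-up will be censored at the last outpatient clinic appointment". Patients discharged alive are censored when a physician last saw them. The second analysis concerns disease progression. Its competing events are discharge, loss to follow-up, death during follow-up and intervention before progression. Its only censoring date is again the last clinic appointment.

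Section 3.7 names Appendix 1 as the data collection tool. Its Surgery page (6) requires a surgery date and an indication. The SRS page (7) and fRT page (8) begin with pre-radiation performance status, and their only date is the item "Scan date (at progression or last follow-up date if no progression". On the discharge/loss page (9) the only unconditional date is that of data entry.

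On eligibility, section 3.1 includes patients "newly-diagnosed over a 2-year period between 1st January 2009 and 31st December 2010". The Appendix 1 check on the initial scan date reads: "YYYY can't be ≤2007 or ≥2011".

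**The concern.** A time-to-event analysis can use only the dates that were collected. The text and the form disagree about which dates those are, and a later analysis plan cannot repair that. Records are anonymised and the link files stay at the sites (sections 3.6 and 4.3), so a date left out of REDCap can be recovered only by going back to each centre.

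Three results depend on the missing items: the cumulative incidence of primary intervention, which pools surgery with radiation; the progression analysis, which must place intervention, discharge and loss in time relative to progression; and follow-up and regrowth times after SRS or fRT. Without a treatment date, surgery would be timed from the operation and radiation from some other date that the protocol does not define.

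**Working it through.** **Dates collected.** Appendix 1 contains these date fields: initial scan (page 2); monitoring scan (page 5); surgery, and scan at recurrence or last follow-up (page 6); scan at progression or last follow-up (pages 7 and 8, one each); data entry, and a rescan date if a rescan took place (page 9); death (page 10).

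**Required items against fields.**

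| Item required or used | Section | Field in Appendix 1 | Nearest substitute |
|---|---|---|---|
| Date of surgery | 3.8.3, 3.10.1 | Yes, page 6 | not needed |
| Date of SRS or fRT | 3.8.3, 3.10.1 | None | Scan at which the treatment was chosen |
| Indication, surgery | 3.8.3 | Yes, page 6 | not needed |
| Indication, SRS or fRT | 3.8.3 | None | None |
| Post-radiation performance status | 3.8.3 | None separate from last follow-up | Status at progression or last follow-up |
| Last clinic appointment | 3.10.1 | None | Last scan date |
| Last physician contact | 3.10.1 | None | Last scan or data-entry date |
| Date of discharge or loss | 3.10.1 | None | Scan whose outcome records it |
| Date of death | 3.10.1 | Yes, page 10 | not needed |

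Treatment-date fields: surgery 1, SRS 0, fRT 0. Section 3.10.1 names two distinct censoring dates, and 0 of 2 are collected. Of the competing events in the progression analysis, death has a date, intervention has one for surgery only, and discharge and loss have none.

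**Quality of the substitutes.** The outcome on a monitoring scan is a decision: the form's own note allows for a treatment that has yet to take place. The scan date therefore marks the decision, not the treatment. If radiation is chosen at the initial management decision (page 4), the only earlier date is the initial scan, and the substitute makes time to intervention zero.

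The widest gap is for a patient discharged at the initial decision, alive and never rescanned. That patient has only the initial scan date and the data-entry date. Assume that data entry falls between the protocol's version date (31 October 2020) and the last month of the timeline (December 2021):

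- shortest gap: 31 December 2010 to 31 October 2020 = 9 years 10 months, about 9.8 years;
- longest gap: 1 January 2009 to 31 December 2021 = 13.0 years.

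The discharge date and last physician contact lie somewhere in that interval, and the form does not say where.

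**Year check.** The eligible window is 365 + 365 = 730 days, which reproduces the stated 2 years. The check accepts 2008, 2009 and 2010, that is 366 + 365 + 365 = 1096 days. The excess is 1096 − 730 = 366 days, and 366/1096 = 33.4% of the accepted window. Rejecting 2008 as well restores 730 days.

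**The case against.** The strongest reply is that the dates are approximate rather than absent. Section 3.8.3 pairs each scan with its clinic appointment, and page 5 pairs each dated scan with an outcome that includes discharge, loss and death. Loss to follow-up rarely has an exact date in any case. This stands in part: for patients under regular monitoring the preceding scan is a usable approximation. But section 3.10.1 names other dates and defines no substitution, and the approximation is poor for patients discharged at the outset. It also supplies no indication for SRS or fRT.

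A second reply is that Appendix 1 is a guide for developers and section 3.7 plans two testing phases, so the live database may already differ. That is possible and cannot be checked here. The protocol as written still contradicts itself.

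A reader might infer that the forms cannot support any of the planned time-to-event work, including the primary validation. The documents do not support that: radiological progression and new symptoms are tied to dated scans, and surgery and death have their own dates. Nor is time to regrowth a secondary objective. Section 2.2 speaks of the risk of recurrence or growth, which the yes/no regrowth item can address; time to regrowth is a variable required by section 3.8.3.

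**Conclusion.** The inconsistency is real and should be fixed. Followed as written, Appendix 1 cannot deliver the cumulative incidence of intervention or the competing-risk analysis of progression on the dates that section 3.10.1 states, nor the post-radiation times and the indication for radiation that section 3.8.3 requires.

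The form omits a treatment date and an indication for every SRS and fRT patient, but the effect on any estimate is unknown. The protocol gives no frequency of SRS, fRT, discharge or loss, and no wait from decision to treatment. It may be tempting to conclude that radiation events would all be dated early by the full wait. That presumes the analyst would use the decision scan, a rule the protocol does not state. Even under that rule, a cumulative incidence at a fixed time changes only through patients whose wait spans that time.

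The year check is a minor mismatch. Eligibility itself is stated consistently as 2009–2010, and the scan date is stored, so a filter would find any 2008 record.

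The conclusion assumes that the live database follows Appendix 1.

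**What to change.** In Appendix 1, add as required fields:

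- pages 7 and 8: date of SRS, or date of first fRT fraction; indication for intervention, with the same options as on page 6; and post-radiation performance status;
- pages 5 and 9: date of last clinic or physician contact;
- page 9: date of discharge or of loss to follow-up.

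As a minor correction, make the initial-scan check reject years up to and including 2008 as well as 2011 onwards, and query any 2008 record already entered.

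The cost is a few REDCap fields, one validation limit and a short extra record lookup per patient. It is lowest before or early in data collection; afterwards, each centre would have to reopen its records.

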2.2. Secondary objectives

- To update the parameters of the prognostic model IMPACT if measures of external validation demonstrate a poor fit
- To determine the growth patterns of incidental meningiomas
- To examine the MRI and pathology features of meningiomas subject to surgical resection
- To determine the risk of post-intervention complications and tumour recurrence/growth for meningiomas subject to surgery, stereotactic radiosurgery, or fractionated radiotherapy
- To assess the economic implications of stratifying follow-up according to risk of disease progression

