Outcome	Dropdown list/check box 
 • Resume follow-up (active monitoring) • Surgery • SRS • fRT • Discharge • Lost to follow-up • Dead 	Required entry. Allow one option only Note to data collector: You will be directed to the relevant page/section dependent on the choice. If the patient died or was lost to follow-up after this interval scan, please choose one of the last two options, albeit the intention might have been to continue monitoring or intervene. If the option you choose is set to take place in the future, choose the option, save the data entered and exit the form with no further information required.
SURGERY (SECTION/PAGE 6)		
Surgery date	DD/MM/YYYY	Required entry
Indication for intervention	Dropdown list/checkbox 
 • Clinical-radiological • Clinical • Radiological • Patient preference 	Required entry. Allow one option only
Preoperative WHO PS	Dropdown list/checkbox 
 • 0 • 1 	Required entry. Allow one option only

	
 • 2 • 3 • 4 	
Preoperative comorbidities	
Check box
 
 • Hypertension - systolic > 140 or diastolic > 90 and patients on medical treatment • Previous myocardial infarction • Congestive heart failure • Peripheral vascular disease • Previous stroke/TIA - If hemiplegia present, do not check • Hemi/paraplegia • Diabetes which requires medical treatment • Diabetes with end-organ damage - if so, do not check diabetes that requires treatment • COPD/Asthma • Renal disease • Mild liver disease - Hep B/C or cirrhosis without portal hypertension • Moderate to severe liver disease - cirrhosis with portal hypertension, jaundice, ascites • Peptic ulcer disease • Cancer - excluding basal cell carcinoma • Metastatic cancer - if so, do not check cancer 	
Required entry. Allow multiple options.
 
Note to data collector: Age and comorbidities will be used to calculate the age adjusted Charlson comorbidity index. Each of these is defined in the guide provided

	
 • Rheumatic or connective tissue disease • HIV/AIDS • Skin ulcers/cellulitis • Depression • Dementia • On Warfarin 	
Simpson grade	Dropdown list/check box 
 • 1-GTR • 2-GTR • 3-GTR • 4-STR • 5-STR 	Required entry. Allow one option only

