Pharmacological intervention	Checkbox	Prompt entry if previous option (Postoperative surgical complications) has been ticked
Surgical intervention	Dropdown list/checkbox 
 • No • Without GA • Under GA 	Prompt entry if previous option (Postoperative surgical complications) has been ticked
ICU admission	Checkbox	Prompt entry if previous option (Postoperative surgical complications) has been ticked
Organ failure	Dropdown list/checkbox 
 • None • Single-organ • Multi-organ 	Prompt entry if previous option (Postoperative surgical complications) has been ticked. Allow one option only
Persisted with no improvement beyond 30 days?	Checkbox	Prompt entry if previous option (Postoperative surgical complications) has been ticked

Postoperative medical complications	checkbox	Required
Complication	Dropdown list/check box 
 • Myocardial infarction • Arrhythmia • Pneumonia • Pulmonary embolism • Deep venous thrombosis • Urinary tract infection • Acute kidney injury • Other 	Prompt entry if previous option (Postoperative medical complications) has been ticked Allow more than one option
Pharmacological intervention	Checkbox	Prompt entry if previous option (Postoperative medical complications) has been ticked
Surgical intervention	Dropdown list/checkbox 
 • No • Without GA • Under GA 	Prompt entry if previous option (Postoperative medical complications) has been ticked
ICU admission	Checkbox	Prompt entry if previous option (Postoperative medical complications) has been ticked
Organ failure	Dropdown list/checkbox 
 • None • Single-organ • Multi-organ 	Prompt entry if previous option (Postoperative medical complications) has been ticked. Allow one option only
Persisted with no improvement beyond 30 days?	Checkbox	Prompt entry if previous option (Postoperative medical complications) has been ticked
Postoperative WHO PS	Dropdown list/checkbox 
 • 0 • 1 • 2 • 3 • 4 • 5 (dead) 	Required. Allow one option only
Recurrence	Checkbox	Prompt entry if previous option (Postoperative WHO PS) is not 5
Scan date (at recurrence or last follow-up date if no recurrence)	DD/MM/YYYY	Prompt entry if previous option (Postoperative WHO PS) is not 5

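### The surgery data set has no item for radiosurgery or radiotherapy given after resection and no written branch to the radiation pages, so recurrence after surgery cannot be split by radiation status and that radiation's dose and toxicity are not captured

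*Protocol*

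**What the plan says.** Protocol 2.2 sets as a secondary objective: "To determine the risk of post-intervention complications and tumour recurrence/growth for meningiomas subject to surgery, stereotactic radiosurgery, or fractionated radiotherapy".

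Section 3.8.3 serves it with two separate lists. The surgery list covers Simpson grade, WHO grade and brain invasion, complications, follow-up duration, performance status and recurrence. Its complication item is "Postoperative medical and surgical complications recorded at 30 days" and its recurrence item is "Recurrence on contrast-enhanced MRI during that time (yes/no) and if recurred then the time to recurrence". Radiation details ("Fractionated dose (fRT), number of fractions (fRT) and total dose (fRT /SRS") and CTCAE toxicity appear only in the list for SRS and fRT.

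Appendix 1 turns this into pages. The surgery page (Page 6) closes with a recurrence tick box, one date field ("Scan date (at recurrence or last follow-up date if no recurrence") and "WHO PS at time of recurrence/last follow-up". The SRS page (Page 7) and then the fRT page (Page 8) follow. Pages are opened by single-choice decision fields, with the note to collectors: "You will be directed to the relevant page/section dependent on the choice".

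**The concern.** The surgery page accepts subtotal resections (Simpson 4 and 5) and WHO grades 2 and 3, so patients with residual or higher-grade tumour are expected in the data. Some operated patients may have had radiation before any recurrence was seen. As the plan is written, such a patient carries the same fields as one treated by surgery alone.

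Two things are then lost for the objective in 2.2. Recurrence after surgery becomes a mixture that cannot be separated. The dose, fractions and toxicity of post-operative radiation, which 3.8.3 wants for SRS and fRT, have no place in that patient's record. This is a gap in data capture, so no later analysis plan can repair it.

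**Working it through.** The plan gives no figure on this point, so the check traces the fields and the routes between pages.

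**1. Items recorded after surgery**
- Section 3.8.3, surgery list: no item for later SRS or fRT.
- Appendix 1, Page 6: surgery date, indication, preoperative performance status and comorbidities, Simpson grade, WHO grade, brain invasion, updated WHO grade, surgical and medical complications, postoperative performance status, recurrence, one scan date, and performance status at that date. There is no radiation item and no outcome or next-treatment field.
- The pharmacological and surgical intervention fields on Page 6 are prompted by a postoperative complication. They do not record tumour treatment.
- Section 3.8.4 records discharge, loss to follow-up, death or continuing follow-up, not treatment.

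**2. Written routes to Pages 7 and 8**
- Page 4, management decision: one option only. Choosing surgery leads to Page 6.
- Page 5, active-monitoring outcome: one option only. Choosing surgery again leads to Page 6.
- Page 9, "Discharge from outpatient care/Lost to follow-up (SECTION/PAGE 9": an outcome field after a rescan, one option only. No written branch leads from Page 6 to Page 9.

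None of the three routes starts from Page 6.

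**3. What can and cannot be separated**

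Let *f* be the share of operated patients irradiated before recurrence, *r0* the recurrence risk with surgery alone and *r1* the risk with surgery plus radiation.

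Pooled risk = (1 − *f*)·*r0* + *f*·*r1*, so pooled − *r0* = *f*·(*r1* − *r0*).

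The form yields only the pooled risk; *f*, *r0* and *r1* are not identifiable from it. The protocol gives none of the three. The sign depends on whether irradiated patients recur less often (an effect of radiation) or more often (selection of higher-risk resections).

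For illustration only, on assumed inputs, the relative difference from surgery alone is *f*·(*r1*/*r0* − 1):
- *f* = 5%, *r1*/*r0* = 0.7: 0.05 × (−0.3) = −1.5%
- *f* = 30%, *r1*/*r0* = 0.3: 0.30 × (−0.7) = −21%
- *f* = 5%, *r1*/*r0* = 2: 0.05 × 1 = +5%
- *f* = 30%, *r1*/*r0* = 2: 0.30 × 1 = +30%

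These values show only that the difference can go either way. They do not estimate it.

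**4. Timing**

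Radiation given after a recorded recurrence does not alter time to first recurrence. Its dose and toxicity are still missing.

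**5. What does not depend on the gap**
- Sample size (3.4): 100 events ÷ 10% = 1,000 patients, which reproduces the plan's figure before it is raised to 1,500. Neither input concerns treatment after surgery.
- Surgical complications are counted at 30 days on a surgical and medical scale that needs no radiation item.
- The validation in 3.10.1 concerns progression of the incidental tumour, not recurrence after resection.

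**The case against.** **The guide is not the database.** Appendix 1 instructs developers, two testing phases follow (3.7), and the flowchart and the management figure are not visible here. The guide also leaves other routes unwritten: Page 6 has no stated branch to the mortality page when postoperative performance status is 5, although 3.8.4 requires deaths to be recorded. Section 3.8.3 says in general terms that details of any intervention performed will be recorded. This stands as a limit on certainty: one cannot say that the live database is unable to hold these data. It does not supply the missing item. The surgery list in the body of the protocol has the same omission, and no repeat entry is described.

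**Only the first treatment is of interest.** The term primary intervention belongs to the cumulative incidence analysis in 3.10.1. The objective in 2.2 concerns what happens after intervention, and Page 6 follows patients to recurrence.

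**The pooled figure is a legitimate quantity.** This is correct. Recurrence in all operated patients under routine care is a reasonable reading of the objective, and it should still be reported. What is lost is the ability to say how much of it reflects surgery alone.

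**Stronger readings that the protocol does not support.**
- A reader might infer that surgical recurrence will be understated by a known amount. Without a rate of post-operative radiation, neither size nor direction can be given. The risk had no one been irradiated is a counterfactual that the objective does not ask for.
- A reader might infer that comparisons by Simpson or WHO grade are confounded. Section 3.10 plans no comparison of recurrence by either grade.
- A reader might infer that irradiated patients are all stored as free of recurrence. Page 6 records a recurrence whether or not radiation was given.

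**Conclusion.** The point holds as a gap in what is collected for one secondary objective. As written, the protocol does not distinguish operated patients who had SRS or fRT afterwards from those who did not, and it provides no place for the dose and toxicity of that radiation. The number of patients affected is not given, so the effect on the recurrence estimate is unknown in size and in sign.

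The conclusion assumes that the built database follows the guide and that some operated patients were irradiated. If neither the live database nor the unseen figures add an item or a route, the information cannot be recovered at analysis. It is worth correcting, but it does not threaten the study's main purpose.

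**What to change.** Add one item to Page 6, and to the surgery list in 3.8.3: SRS/fRT after surgery: none / before recurrence / at or after recurrence, with type and date. Open Page 7 or Page 8 when either of the last two is chosen. The date matters because Pages 7 and 8, as listed, have no treatment-date field of their own.

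Report recurrence after surgery overall, and separately for surgery alone and surgery plus radiation before recurrence. Report the toxicity of post-operative radiation with the SRS/fRT results, but distinguishable from that of primary SRS/fRT.

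This records care already given and sets no treatment rule. It needs one field and a branch to existing pages, and investigators already have the records open. The cost is slightly more data entry for operated patients and wider intervals for the split estimates.
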